9.2.1. Reactogenicity Assessments: Symptom Memory Aide (SMA)

Fourteen (14) different reactogenicity symptoms (including other/specify) are collected pre-IP administration and once daily for the 7 days following each of the IP administrations via a "Symptom Memory Aide (SMA)", see Protocol Appendix 5. Symptoms are reported by the subject, at 4 levels of intensity (0=None, 1=Mild, 2=Moderate, 3=Severe).

Each symptom will be summarized by severity (worst reported over the course of the 7 days) by treatment and whether subjects experienced a given symptom at any severity. This summary will be done for IP administration 1 and repeated for IP administration 2. Symptom category "other" will be included in the listings only.

Each symptom will be summarized by the number of days with symptoms for each subject. This summary will be done for IP administration 1 and repeated for IP administration 2. Symptom category "other" will be included in the listings only.

Each symptom (and oral temperature) will be summarized by IP administration (1 or 2) and timepoint (Day 1 pre-dose (coded as Day 0), Day 1 post dose, Days 2-7). Summary statistics will be given for oral temperature (mean, SD, median, min, max) and as yes/no (0,1, missing) for each symptom. Symptom category "other" will be included in the listings only.

These summaries will use the EVAL set.

SMA symptoms will not be grouped into local and/or systemic events.

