9. ADVERSE EVENT REPORTING

9.1. Definitions

Adverse Event

An AE is any untoward medical occurrence in a clinical study subject administered a medicinal (investigational or non-investigational) product. An AE does not necessarily have a causal relationship with the treatment. An AE can therefore be any unfavorable and unintended sign (including an abnormal finding), symptom, or disease temporally associated with the use of a medicinal (investigational or non-investigational) product, whether or not related to that medicinal (investigational or non-investigational) product.

This includes any occurrence that is new in onset or aggravated in severity or frequency from the baseline condition, or abnormal result of diagnostic procedures, including clinical laboratory test abnormalities.

AEs will be monitored continuously from the first administration of IP treatment until Day 57. SAEs or medically attended events will be documented until Day 209. Events recorded at the follow-up phone call will be assessed and followed up as appropriate.

Serious Adverse Event

An SAE is any untoward medical occurrence that meets any of the following conditions:

- results in death;
- is life-threatening, i.e., the subject was at risk of death at the time of the event (e.g., ventricular fibrillation and anaphylaxis). The term does not refer to an event which hypothetically might have caused death if it were more severe.
- requires inpatient hospitalization or prolongation of existing inpatient hospitalization:
 - Hospitalization refers to an overnight admission into hospital for the purpose of investigating and/or treating the AE. Hospitalization for an elective procedure, or routinely scheduled treatment for a pre-existing condition that has not worsened, is not an SAE.
- results in persistent or significant disability/incapacity, i.e., causing substantial disruption of the subject's ability to conduct normal life;
- is a congenital anomaly/birth defect;
- is medically significant, i.e., may not be immediately life-threatening or result in death or hospitalization but may jeopardize the subject's health or may require intervention to prevent one of the above outcomes. Examples of such events are intensive treatment in an emergency room or at home for allergic bronchospasm, blood dyscrasias, or convulsions that do not result in hospitalization or development of drug dependency or drug abuse.

Unlisted (Unexpected) Adverse Event

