9.4. Reactogenicity

Reactogenicity events may be common and are known to occur for the vaccine being studied and will be collected as solicited AEs in a standard, systematic format using a grading scale based on functional assessment or magnitude of reaction. In this study, the following reactogenicity events will be collected for the first 7 days after each dose of IP:

- Feverish
- Nasal irritation
- Nasal bleeding
- Runny nose
- Stuffy nose/Congestion
- Sore/scratchy/itchy or painful throat
- Body/muscle aches
- Joint pain
- Headache
- Cough
- Body rash
- Tiredness
- Nausea
- Vomiting
- Other symptoms

These will be evaluated and graded daily based on the functional scale specified within the Symptom Memory Aid ([Appendix 5](#)).

Should a subject experience a severe reaction (graded as a 3) and/or measure a body temperature equal to or greater than 39°C, he/she should immediately contact the site.

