9.3. Clinical Laboratory Evaluation

A central clinical laboratory will be used for this study. Laboratory-based AEs will be reported based on the Grading Scale for Laboratory AEs – Modified from FDA Grading Scale as Appropriate for Local Lab (Protocol Appendix 2).

Summary statistics of test results and change from Baseline test results will be done for all serum chemistries and hematology.

For serum chemistries and hematology, and urinary assessments where FDA vaccine grading scale is applicable (Protocol Appendix 2), maximum shift from Baseline in severity will be provided.

Urinalysis (dipstick) results will be listed and not summarized.

A listing of clinical laboratory test results outside the reference ranges will be provided.

Clinically significant (CS) values or CS change from baseline values were to be recorded as AEs at the discretion of the clinical and safety monitor.

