9.4. Vital Signs

Blood pressures, heart rate, respiratory rate and temperature will be summarized at each time point by descriptive statistics for the result and for the change from baseline

CS values or CS change from Baseline were recorded as AEs at the discretion of the clinical investigator.

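### The diary tables of worst severity and symptom days ignore the subject's own pre-dose score, so symptoms persisting from before dosing are counted in full

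*SAP*

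**What the plan says.** SAP 9.2.1 states that the diary symptoms "are collected pre-IP administration and once daily for the 7 days following each of the IP administrations". It then plans three summaries for each administration:

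- Severity and occurrence: "Each symptom will be summarized by severity (worst reported over the course of the 7 days) by treatment", together with whether the subject had the symptom at any severity.
- Duration: "Each symptom will be summarized by the number of days with symptoms for each subject".
- A yes/no table by "timepoint (Day 1 pre-dose (coded as Day 0), Day 1 post dose, Days 2-7".

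Only the third shows the pre-dose entry, and it does so as a percentage of the group. Protocol 8.3.3 asks for the same three kinds of diary summary and sets no baseline rule either.

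Other safety data are referred to baseline. For laboratory grades, SAP 9.3 says "maximum shift from Baseline in severity will be provided". Vital signs in SAP 9.4 are "summarized at each time point by descriptive statistics for the result and for the change from baseline". SAP 9.2 lists AEs that began before the first administration but leaves them out of the AE summaries. Protocol 9.1 says of the AE definition: "This includes any occurrence that is new in onset or aggravated in severity or frequency from the baseline condition". Protocol 9.4 says reactogenicity events "will be collected as solicited AEs in a standard, systematic format".

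**The concern.** Read literally, the severity and duration summaries cannot separate a symptom that began after dosing from one the subject already had. A subject with a mild runny nose before dosing and the same mild score on every later entry appears as a mild runny nose lasting 7 days. A subject whose tiredness was 2 before dosing and 1 afterwards also appears as a case. The by-timepoint table does not help, because it does not show whether the subjects with symptoms after dosing are the ones who had them at Day 0.

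Tolerability of one and two administrations is a primary objective, and Protocol 8.3.3 names subject diaries among its sources. SAP 9.2 says diary symptoms and AE reports were not reconciled, so investigator review does not correct the diary tables. At stake is how the absolute symptom rates and durations in each arm are read.

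**Working it through.** **The plan's own figure.** There is none to reproduce. The sample size is empirical, no hypothesis is tested, and neither document gives a rate of pre-dose symptoms. The finding itself is textual; the arithmetic only illustrates its size.

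**Inputs**
- n = 40 per arm: SAP 12 reports that enrolment stopped at approximately this number.
- b, the share of subjects with a given symptom before dosing that persists into a post-dose entry: assumed 5% or 10%.
- p, the new-onset rate after dosing: assumed 10% on placebo and 35% on vaccine, independent of b.

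**Rate shown by the planned table** = b + (1 - b) x p
- b = 5%, placebo: 0.05 + 0.95 x 0.10 = 14.5%
- b = 5%, vaccine: 0.05 + 0.95 x 0.35 = 38.25%
- b = 10%, placebo: 0.10 + 0.90 x 0.10 = 19.0%
- b = 10%, vaccine: 0.10 + 0.90 x 0.35 = 41.5%

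**Extra subjects counted** = n x b x (1 - p)
- Placebo: 40 x 0.05 x 0.90 = 1.8; 40 x 0.10 x 0.90 = 3.6
- Vaccine: 40 x 0.05 x 0.65 = 1.3; 40 x 0.10 x 0.65 = 2.6

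**Contrast.** The expected risk difference is multiplied by (1 - b).

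| b | Placebo | Vaccine | Risk difference (points) | Relative risk |
|---|---|---|---|---|
| 0 | 10% | 35% | 25 | 3.5 |
| 5% | 14.5% | 38.25% | 23.75 | 2.6 |
| 10% | 19% | 41.5% | 22.5 | 2.2 |

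If the two arms share the same new-onset rate, the expected difference stays zero. At b = 10% and p = 20% in both arms, each shows 0.10 + 0.90 x 0.20 = 28%.

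**Symptom days.** Each carried-in subject can add up to 7 days. The expected number of such subjects per arm is 40 x 0.05 = 2 or 40 x 0.10 = 4, so at most 14 or 28 days per arm for that symptom.

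**Chance imbalance.** The 95% range for the between-arm difference in the carried-in share is 1.96 x sqrt(2b(1 - b)/n).
- b = 5%: 1.96 x sqrt(2 x 0.05 x 0.95/40) = 9.6 points
- b = 10%: 1.96 x sqrt(2 x 0.10 x 0.90/40) = 13.1 points

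These use a normal approximation that is rough at 2 to 4 expected subjects. The effect on the tabulated rates is smaller, because a carried-in subject changes the count only if he or she would not have had a new symptom anyway.

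**Is there a pre-dose score at dose 2?** SAP 9.2.1 implies one at each administration, although it labels the time point as Day 1. Protocol 6.2.1.6 and the Day 1 procedures (6.1.2.1) describe a pre-dose entry at the first dose, as training. The Day 29 procedures (6.1.2.4) mention only handing out the diary with instructions. Appendix 5 shows the first-dose form, with a training column, and says a similar form will be used for the second dose. The documents do not settle the question.

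**The case against.** The strongest case for leaving the plan alone is that tabulating every symptom after dosing beside a concurrent placebo is a defensible convention. Protocol 3.5.3 gives placebo the role of showing what happens without vaccination, and the SAP delivers the three diary summaries that Protocol 8.3.3 asks for. Pre-dose prevalence is visible by arm at Day 0, and subject listings are planned. The population is healthy, significant rhinitis is excluded at the investigator's discretion, and minor illness must resolve before enrolment. This stands as a reason to keep the planned tables as the main display. It does not supply the missing within-subject link: placebo shows the background rate but does not separate persisting from new symptoms in an arm's severity or duration distribution.

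Several stronger readings are tempting, and the documents do not support them:

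- *The primary endpoint is inflated.* It consists of vaccine-associated AEs and SAEs, based on investigator assessment of relatedness. SAP 9.2 says a diary symptom may or may not have become an AE.
- *The results are biased for or against vaccine.* Randomisation makes carry-in equal across arms in expectation. It shrinks a true difference slightly and does not create one.
- *The tables breach the AE definition.* Protocol 9.1 words new or aggravated events as something the definition includes, and these tables report symptoms rather than AEs.
- *Dose 2 is affected more because the influenza season advances.* No document gives a pre-dose rate at either dose, and laboratory-confirmed influenza excludes a subject from the second dose.
- *The main table should be replaced by a subtraction rule.* One pre-dose entry would then override a week of evening entries and could hide a true reaction. If dose-2 pre-dose scores are absent and raw scores are used instead, dose 1 would be corrected and dose 2 would not, which would create an artefact in that comparison.

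**Conclusion.** The point holds as a gap in the supportive diary analysis. A pre-dose score is described, the worst-severity and symptom-day tables do not use it, and the by-timepoint table shows it only at group level. Symptoms that persist from before dosing are therefore included in full. The consequences are higher absolute rates and longer durations in all arms, a slightly diluted vaccine-placebo contrast, and some chance imbalance.

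Under the assumed inputs, the effect for one symptom is 1.8-3.6 extra placebo subjects and 1.3-2.6 extra vaccine subjects per 40. The placebo rate nearly doubles at 10% carry-in, while the risk difference loses only 1.25 to 2.5 points. These sizes rest wholly on the assumed rates and on carry-in being independent of new onset. If few subjects had symptoms before dosing, the effect is negligible, and the proposed tables would show that.

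**What to change.** In SAP 9.2.1, keep the planned tables as the main display and add the following by treatment and dose, among subjects with a pre-dose score for that dose:

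1. For each symptom, a within-subject shift table from the pre-dose score to the worst score from Day 1 post-dose to Day 7.
2. The number and percentage of subjects whose worst post-dose score exceeds their pre-dose score (new or worsened).
3. The number of days above the pre-dose score.

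State in the SAP whether a pre-dose score was collected before the second dose. If it was not, give the baseline-referenced tables for dose 1 only, and compare dose 1 with dose 2 on the unadjusted tables. Report how many subjects lack a pre-dose score at each dose.

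The cost is SAP wording, a derived variable and a few supportive tables; no new data are needed where the pre-dose entry exists. The downside is that the new-or-worsened version can under-count a true reaction in a subject who happened to have a transient symptom at the pre-dose entry, which is why it should sit beside the planned tables and not replace them.

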6.2.1.6. Symptom Memory Aids

Subjects will be asked to record post-treatment symptoms in a Symptom Memory Aid ([Appendix 5](#)) at the time points specified in the Schedule of Events ([Table 3](#)) for reactogenicity. At time of first dose, the first entries will be in concert with study staff as a training session at pre-dose, the second entry will be the evening of vaccination and subsequent 6 entries will be made each evening following the IP delivery. Since visit Day 36 may occur ± 1 day, the subject may not complete all days listed on the memory aid prior to the first post-dose visit. For subjects who attend the clinic at Day 35, a stamped and pre-addressed envelope will be provided so that the diary may be completed and mailed to the Site. Symptoms recorded on diaries returned by mail will be reviewed with the subject by telephone, if needed. Subject diaries will be retained as source documents.

Events that are reported in the Symptom Memory Aid will be reviewed by the study staff and assessed and recorded as AEs according to the appropriate toxicity scale ([Appendix 1](#) for vital signs and systemic AEs and [Appendix 3](#) for reactogenicity assessments). During this time, subjects are asked to take their oral temperature (at approximately the same time each evening using the thermometer provided to them by the site) and record it in the Symptom Memory Aid. Any medications taken by the subjects will also be recorded in the Symptom Memory Aid. In addition,

subjects will be asked to record symptoms they may be experiencing during this time period, including:

- Feverish
- Nasal irritation
- Nasal bleeding
- Runny nose
- Stuffy nose/Congestion
- Sore/scratchy/itchy or painful throat
- Body/muscle aches
- Joint pain
- Headache
- Cough
- Body rash
- Tiredness
- Nausea
- Vomiting
- Other symptoms

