HOW TO TAKE YOUR TEMPERATURE

- Measure your temperature at approximately the same time each day. If multiple temperatures are measured in one day, record the highest temperature. Do not eat, drink, or smoke for 10 minutes prior to taking your temperature.
- Push the power button on the thermometer and place it under your tongue toward the back of your mouth. The tip of the thermometer should rest in the “correct area” as shown in the diagram to the right.
- Keep your mouth closed and the thermometer still until the thermometer beeps rapidly, indicating completion. If you do not hear the beep, leave the thermometer in your mouth for 2 minutes.
- Record the temperature displayed on the screen. Press the button to turn the thermometer off.

√= Correct Area
X=Incorrect areas

For all symptoms, record the intensity level (0, 1, 2, or 3) using the guidelines below.

SYMPTOM	INTENSITY LEVEL	DESCRIPTION
Feverish Tiredness Body/Muscle aches Joint Pain Body Rash	0	No symptoms
	1	Mild - No interference with activity
	2	Moderate - Some interference with activity
	3	Severe - Significant interference, prevents daily activity
Stuffy Nose/Nasal Congestion	0	No symptoms
	1	Mild - Noticeable but does not interfere with daily activity
	2	Moderate - Moderate discomfort/interferes with breathing from nose
	3	Severe - Not being able to breath from nose, or prevents daily activity or seeks medical encounter
Runny Nose	0	No symptoms
	1	Mild - Noticeable but does not interfere with daily activity
	2	Moderate - Moderate discomfort/interferes with daily activity
	3	Severe - Significant discomfort/prevents daily activity or seeks medical encounter
Nasal Pain/Irritation/Dryness	0	No symptoms
	1	Mild - Noticeable but does not interfere with daily activity
	2	Moderate - Moderate discomfort/interferes with daily activity
	3	Severe - Significant discomfort/prevents daily activity or seeks medical encounter
Nasal Bleeding	0	No symptoms
	1	Mild - Total duration of all episodes in a 24-hour period <30 minutes
	2	Moderate - Total duration of all episodes in a 24-hour period ≥ 30 minutes
	3	Severe - Any bleeding that required visit for medical encounter
Sore/Scratchy/Itchy or Painful Throat	0	No symptoms
	1	Mild - Noticeable but does not interfere with eating and/or drinking
	2	Moderate - Moderate discomfort. Interferes with eating and/or drinking
	3	Severe - Significant discomfort/prevents eating and/or drinking or seeks medical encounter
Headache	0	No symptoms

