9.2. Adverse Events (AEs)

Adverse events were to be recorded from informed consent through Day 57 + 28 days. For subjects receiving only one IP administration, follow-up was 28 days. Serious adverse events were recorded through Day 209. During the study treatment period (through Day 57) subjects were asked non-leading questions to determine the occurrence of spontaneously reported (unsolicited) AEs.

Symptoms were collected for the 7 days following each IP administration using Symptom Memory Aids (SMA), with clinical interpretation by the site investigators. A symptom recorded by the subject on the Symptom Memory Aid (SMA) may or may not have been reported as a solicited AE. For clinical interpretation Investigators used the, "Instructions to site investigators on assessing AEs from symptom memory aids (16 October 2019)" as a guideline in assessing whether a symptom was to be reported as an AE. The investigator was responsible for determining the severity and the relationship to IP for these SMA-based (solicited) AEs. There was no reconciliation of the database between the SMA symptoms and adverse event reports.

Symptom Memory Aids were used to facilitate assessment of AEs, as described in Protocol Section 6.2.1.6. Events that were reported in the Symptom Memory Aid were reviewed by the study staff and assessed and recorded as AEs. Investigators were instructed to clinically assess, and record individual symptoms reported by subjects as AEs in order to ensure that all reactogenicity events were captured. However, Protocol Section 9.6 states "Whenever possible, diagnoses should be given when signs and symptoms are due to a common etiology (e.g., cough, runny nose, sneezing, sore throat, and head congestion should be reported as "upper respiratory infection"). After medical review of the AE listing, it appears that some AEs should be grouped as diagnoses. For example, a subject who reported concurrent cough, runny nose, and sneezing assessed by the investigator as unrelated to vaccine should have those symptoms grouped as a syndromic diagnosis (URI), with the severity based on the most severe

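### The planned diary tables do not give the number of subjects with measured, graded fever after each dose

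*SAP*

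**What the plan says.** SAP 9.2.1 plans three diary summaries, each given separately for dose 1 and dose 2.

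- **Worst severity:** "Each symptom will be summarized by severity (worst reported over the course of the 7 days) by treatment".
- **Duration:** the number of days with each symptom.
- **By day:** "Each symptom (and oral temperature) will be summarized by IP administration (1 or 2) and timepoint". The content for temperature is "Summary statistics will be given for oral temperature (mean, SD, median, min, max"); each symptom is shown as present or absent.

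Measured temperature is named only in the by-day summary. Symptoms are on a different scale: "Symptoms are reported by the subject, at 4 levels of intensity (0=None, 1=Mild, 2=Moderate, 3=Severe"). The item for feeling feverish is one of them. Protocol Appendix 5 grades it by its effect on activity (level 1 reads "Mild - No interference with activity"), not by degrees.

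Protocol Appendix 1 does have a temperature scale: Grade 1 from 38.0 to 38.4 °C, Grade 2 from 38.5 to 38.9, Grade 3 from 39.0 to 40, Grade 4 above 40. Protocol 6.2.1.6 brings it in when diary events are "assessed and recorded as AEs according to the appropriate toxicity scale", and SAP 9.2 applies it to adverse events. No diary table uses it. SAP 9.4 gives clinic-visit temperature descriptive statistics only.

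**The concern.** Fever is a threshold event in a few subjects, so its natural summary is a count by grade. The protocol collects what is needed. Temperature is taken every evening for 7 days after each dose, and if several readings are taken in a day the highest is recorded. The protocol also treats the grades as meaningful: 39 °C or more triggers a call to the site (Protocol 9.4), and the halting rules count Grade 3 and Grade 4 vital signs (Protocol 7.3).

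The primary objectives concern safety after one and after two administrations, and Sing2016 M2SR is first-in-human here. The sponsor describes its earlier studies by individual fevers and by the 38 °C threshold (Protocol 1.4.1 and 1.4.3). If measured fever appears only as daily continuous statistics, a reader of the diary tables cannot state the corresponding figure per dose and arm for this study.

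**Working it through.** The plan gives no figure to reproduce: the sample size was chosen without a formula, and no fever rate is assumed. The checks concern what the planned outputs can show.

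**1. Which outputs could carry fever?**

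| Output | Measured temperature? | Count of subjects by fever grade? | Split by dose? |
|---|---|---|---|
| Diary, worst severity (SAP 9.2.1) | No; subjective feverishness only | No | Yes |
| Diary, days with symptom (SAP 9.2.1) | No; subjective feverishness only | No | Yes |
| Diary, by day (SAP 9.2.1) | Yes; mean, SD, median, min, max | No | Yes |
| Clinic vital signs (SAP 9.4) | Yes; descriptive statistics | No | By visit |
| Adverse event tables (SAP 9.2) | Only if entered as an adverse event | Yes, as pyrexia by maximum severity | None stated |

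**2. Do the five statistics fix the count on one day?** Group size is about 40 (SAP 12). Three illustrative sets of 40 values on a 0.1 °C grid were built and graded with the Appendix 1 cut-points. The five statistics agree to the precision shown.

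| Set | Mean | SD | Median | Min | Max | Grade 1 / 2 / 3 | Subjects at 38.0 °C or more |
|---|---|---|---|---|---|---|---|
| A | 36.80 | 0.70 | 36.6 | 36.0 | 39.2 | 0 / 0 / 1 | 1 (1/40 = 2.5%) |
| B | 36.80 | 0.70 | 36.6 | 36.0 | 39.2 | 1 / 0 / 1 | 2 (2/40 = 5%) |
| C | 36.80 | 0.70 | 36.6 | 36.0 | 39.2 | 2 / 1 / 1 | 4 (4/40 = 10%) |

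The printed rows would be identical, so the count is not determined. The maximum gives only the highest grade reached.

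**3. Do the seven daily rows fix the count over the week?** No. Exchanging values between subjects within a day leaves every statistic for that day unchanged. Four febrile readings on four different evenings could therefore come from one subject (1/40 = 2.5%) or from four (4/40 = 10%), with the same table either way.

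**4. Is fever invisible in the planned table?** No. Assume 4 of 40 subjects at 38.5 °C against a usual 36.7 °C, with an SD of 0.3 to 0.5 °C. These values are assumptions, not from the documents.

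- All on one evening, the mean shifts by 4 × (38.5 − 36.7)/40 = 0.18 °C. The SE of an arm difference is SD × √(2/40) = 0.067 to 0.112 °C, so the shift is 0.18/0.112 = 1.6 to 0.18/0.067 = 2.7 SEs.
- The fevers also raise that arm's SD to √(SD² + 0.1 × 0.9 × 1.8²) = 0.62 to 0.74 °C. With that SD in one arm, the shift is about 1.3 to 1.7 SEs, but the rise in the SD column is itself a sign.
- Spread evenly over seven evenings, the mean shifts by about 0.18/7 = 0.026 °C per row, well under one SE. The maximum still prints 38.5 °C on each evening that has a fever.

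**5. What would a count give?** Exact 95% intervals at n = 40, with illustrative counts: 0/40, 0 to 8.8%; 1/40, 0.1 to 13.2%; 4/40, 2.8 to 23.7%.

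**The case against.** The best reply is that graded fever already has a table. SAP 9.2 says investigators were told to record individual diary symptoms as adverse events so that reactogenicity was fully captured. It grades events on Appendix 1, names pyrexia among the coded terms, and tabulates by preferred term and maximum severity. Readings of 39 °C or more prompt immediate contact with the site. Feverishness is counted per dose by worst severity. Protocol 8.3.3 asks for diary symptoms by time point, worst occurrence and days, which the SAP delivers for symptoms. By-subject listings are also promised (Protocol 8.1).

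Most of this stands and limits the point. A reader might infer that fever appears in no planned table; the adverse event tables rule that out. But SAP 9.2 also says a diary symptom may or may not have become an adverse event, and that "There was no reconciliation of the database between the SMA symptoms and adverse event reports". It states no split by dose. In the secondary presentation, pyrexia judged unrelated can be absorbed into an upper respiratory infection when at least three listed terms coincide. Feverishness is not temperature, and a listing has to be counted by hand.

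A reader might also infer that a fever rate of, say, 10% would go unseen. The documents do not support this: the daily maximum and SD are planned, and fevers on one evening would shift the mean by more than one SE under the assumptions above.

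Past experience suggests small numbers: two self-reported fevers among 96 subjects in the first study, one on vaccine and one on placebo, and none of 38 °C or more before challenge in the Phase 2a study. With so few, the daily maximum tells much of the story. Those data are for single doses of Bris10 M2SR, so they do not settle the matter for Sing2016 M2SR.

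**Conclusion.** The point holds in a limited form. No planned diary or vital-sign table gives the number of subjects who reached an Appendix 1 fever grade in the 7 days after each dose, and that number cannot be derived from the statistics that are planned. Subjective feverishness and adverse-event pyrexia cover part of the ground, but neither is a complete per-dose count of measured fever.

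In the illustrations, the same printed values are compatible with anything from 2.5% to 10% febrile at n = 40. That range depends on the constructed sets; that the count is undetermined does not. Sample size, error rates and study conduct are unaffected, and the SAP does not breach the protocol here. This is a small improvement to the reporting of the primary safety objective.

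**What to change.** In SAP 9.2.1, add one table: N (%) of subjects by maximum recorded oral temperature in the 7 days after each dose, in the Appendix 1 fever grades, by arm and separately for dose 1 and dose 2.

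- **Denominator:** for each dose, Safety Set subjects who received that dose and have at least one post-dose diary temperature. The whole Safety Set would be wrong for dose 2, because it requires only one administration. The Evaluable Set, used for the other diary tables, requires both doses and would drop a subject who was febrile after dose 1 and received no second dose.
- **Keep** the continuous summary.
- **Footnote:** state that the count may differ from adverse-event pyrexia because the two sources were not reconciled, and that the population differs from the other diary tables.

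The cost is one table and a footnote. The readings and cut-points already exist, so no new data are needed.
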